#### **4.7 HANDLING OF WITHDRAWALS**

Patients discontinuing study medication during DPC period will be followed-up for per protocol and return for all scheduled visits through Week 36. In case the patient is lost-to-follow-up or withdraws consent to attend the remaining study visits, all efforts should be made to invite the patient to attend EOT visit as soon after their last dose of study medication and to attend a follow up visit 36 weeks after Baseline. Patients discontinuing OLE period. will be followed for 12 weeks after their last octreotide capsules dose.

Patients will be asked to agree that study assessments be performed as stated in the protocol for the remaining study visits, even if the patient discontinues treatment by his/her decision, or that of the Principal Investigator.

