#### **5.4 END OF TREATMENT (EOT) VISIT**

End of Treatment (EOT) visit is scheduled for patients who discontinued study medication prematurely during DPC period and OLE period. This visit may be performed on a same day as originally scheduled visit or could be scheduled separately. Data collection for this visit should primarily be guided according to principles to protect patient safety and wellbeing.

All efforts should be made to continue and follow up, per protocol until week 36 (including all in-clinic visits and assessments as detailed in DPC Schedule of Assessments) all patients who early

---

 .For a patient with a single visit IGF-1 level  $\geq 1.3 \times$  ULN, a second sample will be obtained within two weeks of the first assessment for a total of 2 consecutive IGF-1 assessments for confirmation of disease activity.

 GH: Five samples collected every  $30 \pm 5$  minutes over two hours, 2-4 hours after study medication administration in the clinic, (patients to fast 4 hours prior to and the 2 hours during GH sampling)

discontinued study medications during the DPC period for any reason.

The following procedures will be conducted at the EOT visit:

- Weight
- Vital signs
- 12-lead ECG
- Laboratory tests: hematology, biochemistry, urinalysis, TSH, free T4, and lipid profile (total cholesterol, triglycerides, high-density lipoprotein, and low-density lipoprotein) and HbA1c; serum pregnancy test in women of childbearing potential
- Physical examination
- Acromegaly directed and treatment directed physical examination
- AEs and concomitant medications recording
- Study medication accountability and compliance assessment
- IGF-1 and GH
- Abdominal (gall bladder) ultrasound
- Complete Early discontinuation/treatment phase completion form, if applicable

Other procedures and evaluations will be completed as deemed necessary by the Investigator after consultation with the medical monitor.

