## 6.9 Safety Analyses

All safety analyses for data collected during the DPC period will be presented using the safety set. All safety analyses for data collected during the OLE will be presented using the OLE set (summaries by treatment group will be based on the treatment group in the DPC period). Safety analyses for the DPC period will only use data collected during the DPC period, and will exclude any safety data that was collected after a subject had discontinued study drug. Safety analyses for the OLE will include data collected during the OLE. No formal hypothesis testing will be conducted. Data will be summarized using appropriate descriptive statistics. Missing data will be maintained as missing, unless indicated.

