### 6.9.5 ECG

All 12-Lead ECGs will be read by a central lab. 12-Lead ECG parameters will be summarized at each time point using descriptive statistics by final dose group and treatment group (i.e., octreotide 40, 60, 80, overall and placebo). Both absolute and change from baseline will be provided for each continuous 12-Lead ECG parameter. Summaries will be provided for the DPC period and for the OLE period. In calculating the change from baseline for both the DPC and for the OLE, the baseline for the DPC period will be used.

Additionally, the numbers and percentages of patients with ECG abnormalities (as determined by the central laboratory) at each visit will be presented for both the DPC and for the OLE. The parameters and abnormality criteria are specified in the table below:

Parameter	Abnormality Criterion
PR interval	<110 ms
	>300 ms
QRS interval	$\geq$ 120 ms
QTcF	<350 ms
	Male >450 ms or Female >470 ms
	>500 ms
Heart rate	<50 bpm
	>110 bpm

Shift tables will be used to show the changes from baseline to each post baseline time point based on the above abnormality criteria for both the DPC and for the OLE periods. For both the DPC period and the OLE period, shifts from baseline will use the baseline defined for the start of the DPC period.

A listing of patients with clinically significant ECG abnormalities (using the high and low cut points above) will be provided in listings.

All tabular summaries will exclude any data that was collected after a subject had discontinued study drug. Data collected after a subject had discontinued study drug will be included in listings.

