### 6.9.6 Abdominal Ultrasound

The following information will be summarized at baseline and end of treatment for the DPC period using shift tables, by final dose group and treatment group (i.e., octreotide 40, 60, 80, overall and placebo):

- Ultrasound Normality (Normal=Yes reported on eCRF; Abnormal = No)
- Biliary Sludge (Normal=No reported on eCRF; Abnormal =Yes)
- Wall Thickening (Normal=No reported on eCRF; Abnormal =Yes)
- Dilatation of Common Bile Duct (Normal=No reported on eCRF; Abnormal =Yes)

For the OLE period, shift tables will also be provided to show shifts from baseline of the DPC period to each assessment in the OLE period.

All tabular summaries will exclude any data that was collected after a subject had discontinued study drug. Data collected after a subject had discontinued study drug will be included in listings.

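### The SAP's exclusion of data collected after study drug is stopped has no window and no EOT exception, so early stoppers can vanish from the ultrasound and ECG tables

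*SAP*

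**What the plan says.** SAP 6.9 states that DPC safety analyses "will exclude any safety data that was collected after a subject had discontinued study drug". SAP 6.9.6 repeats the rule for ultrasound: "All tabular summaries will exclude any data that was collected after a subject had discontinued study drug". The same sentence closes 6.9.3 (laboratory), 6.9.4 (vital signs) and 6.9.5 (ECG). Each of these sections then adds: "Data collected after a subject had discontinued study drug will be included in listings".

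The ultrasound table is defined in SAP 6.9.6: "The following information will be summarized at baseline and end of treatment for the DPC period using shift tables". The ECG tables in SAP 6.9.5 run by visit: "Shift tables will be used to show the changes from baseline to each post baseline time point based on the above abnormality criteria".

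Protocol 5.4 says that the EOT "visit is scheduled for patients who discontinued study medication prematurely during DPC period and OLE period". Its procedures include a 12-lead ECG and a gall bladder ultrasound. On timing it says: "This visit may be performed on a same day as originally scheduled visit or could be scheduled separately". For patients lost to follow-up or withdrawing consent, Protocol 4.7 asks that they be invited to "attend EOT visit as soon after their last dose of study medication".

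Protocol 8.4.8 and 8.4.8.4 contain no exclusion of data collected after discontinuation. SAP section 1 says that the SAP prevails where the two differ.

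**The concern.** The ultrasound table is meant to show the shift from baseline to end of treatment. For a patient who stops early, the assessment that supplies that value is the EOT ultrasound, and the exclusion can remove it because the patient has by then stopped the drug. The same applies to the EOT ECG.

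Patients do not leave these tables at random. Protocol 7.6 says that octreotide raises the risk of gallbladder sludge and stones, and it provides for stopping study drug in the face of severe or persistent gastrointestinal symptoms and certain liver abnormalities. Patients with such problems are among those most likely to have no post-baseline entry. Stopping under the pre-defined withdrawal criteria depends on disease control, so the selection may also differ between arms. Clinically significant ultrasound findings and ECG changes are both listed safety endpoints (SAP 5.2).

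**Working it through.** The plan states no figure on this point, so there is none to reproduce. The check is a trace of the visit schedule against the exclusion rule, followed by a scale illustration on stated assumptions.

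**1. DPC schedule against the rule** (Protocol 4.7, 5.1, 5.2.3, 5.4 and Appendix A; SAP 6.9, 6.9.5 and 6.9.6)

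| Planned ultrasound and ECG | Completer on study drug | Early stopper, EOT after last dose |
|---|---|---|
| Screening | in tables | in tables |
| EOT visit | not applicable | excluded |
| Week 36 | in tables | excluded (off drug) |
| Planned post-baseline values in tables | 1 of each | 0 of each |

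If the EOT visit counts as taking place at or before discontinuation, the early stopper's EOT value could be kept. The documents do not settle this. Neither discontinuation nor end of treatment is defined for these tables. The nearest definition, in SAP 6.9.2.1 for adverse events, equates end of treatment with the last dose of blinded drug.

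**2. Visit mapping.** SAP 6.2 analyses data by nominal visit and lists no EOT visit for either period. Because ECG is tabulated by time point, an EOT ECG has no row to enter even if the exclusion did not apply.

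**3. Adverse event tables as a backstop.** DPC treatment-emergent events end at the last dose (SAP 6.9.2.1). A finding first seen at a later EOT ultrasound, with that date as onset, is not counted. A patient who stopped for a reason other than the withdrawal criteria cannot enter the OLE (Protocol 4.6.1), so the finding is not tabulated there either.

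**4. OLE ECG.** Protocol 5.3 lists no ECG among the OLE visit procedures. In Appendix A the only ECGs after OLE entry are at EOT and Follow-up. EOT is held because the drug was stopped, and Follow-up comes four weeks later. SAP 6.9.5 nevertheless promises OLE summaries and shift tables under the same exclusion.

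**5. Scale, on assumptions.** Planned size is about 50, or about 25 per arm (SAP 3.2). Assume a proportion d stops early and every EOT visit falls after the last dose.

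- Patients with no planned post-baseline entry = 50 × d. For d = 10%, 20%, 30% and 40% this gives 5, 10, 15 and 20.
- Patients retained per arm, 25 × (1 − d), rounded: 23, 20, 18 and 15.
- Chance that an arm's table shows at least one event = 1 − (1 − q)^n, with the same true rate q in stoppers and completers:

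| True rate q | n = 25 | n = 23 | n = 20 | n = 18 | n = 15 |
|---|---|---|---|---|---|
| 5% | 72.3% | 69.3% | 64.2% | 60.3% | 53.7% |
| 10% | 92.8% | 91.1% | 87.8% | 85.0% | 79.4% |

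- If stoppers have a different rate, the table understates the arm's rate by d × (stopper rate − completer rate). With an assumed 25% in stoppers and 10% in completers, d = 30% gives a true rate of 0.70 × 10% + 0.30 × 25% = 14.5%, against 10% in the table. Over d = 10% to 40% the shortfall is 0.10 × 15 = 1.5 to 0.40 × 15 = 6.0 percentage points. If the two rates are equal it is zero.

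**The case against.** The strongest reply is that tabulating on-treatment safety data is a legitimate choice. Protocol 8.4.8.1 already limits DPC treatment-emergent events to the last dose. Patients who meet the withdrawal criteria are rescued with an injectable SRL, so off-drug values could credit that drug's biliary effects to placebo. This stands as a reason to keep later off-drug visits out of the tables. It does not justify losing an assessment made close to the last dose.

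It can also be said that the EOT visit may fall on a dosing day. Protocol 5.4 allows it to share a day with a scheduled visit, and its GH footnote refers to dosing in the clinic. That makes exclusion uncertain for an individual patient. However, Protocol 5.7.1 allows for no clinic dosing, and Appendix A shows no on-site administration at EOT. Inclusion would then depend on how the visit was scheduled.

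The excluded data remain in listings, and with about 50 patients and no formal safety testing they can be reviewed there. Adverse events up to the last dose are tabulated, including those leading to discontinuation. Both facts limit the harm, but neither repairs the shift table.

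The shortage of OLE ECGs comes first from the visit schedule. The exclusion then removes most of what the schedule leaves.

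**Conclusion.** The concern holds in a limited form. On a literal reading, an early stopper whose EOT visit follows the last dose has no planned post-baseline ultrasound or ECG in the DPC tables. The OLE ECG summaries have almost no eligible data. The size is unknown, because the documents give neither a discontinuation rate nor an event rate for this trial. The 5 to 20 of 50 patients and the shortfall of 1.5 to 6.0 points rest wholly on the assumptions stated.

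Several stronger inferences are tempting, and the documents do not support them:

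- That the SAP discards post-discontinuation safety data: they are listed.
- That the EOT assessments are an early stopper's only on-study ones: a Week 36 ultrasound and ECG are also planned, and Protocol 5.8.6 allows repeat ultrasounds. EOT is the only planned post-baseline assessment tied to stopping.
- That removal is certain in every case: it depends on visit timing and on undefined terms.
- That an end-of-treatment ECG table is affected: ECG is tabulated by time point, and the gap there is compounded by the missing EOT visit in SAP 6.2.
- That laboratory and vital-sign tables suffer equally: these are measured at every DPC clinic visit, so a patient who reached one on drug keeps a value.

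This is a safety-table correction worth making before unblinding. It does not bear on the primary efficacy conclusion, and that conclusion does not depend on it.

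**What to change.** Amend the SAP as follows:

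- **6.9, 6.9.5 and 6.9.6:** for ultrasound and ECG, define the end-of-treatment value as the last post-baseline assessment up to and including the EOT visit, within a window after the last dose that is stated before unblinding.
- **6.2:** add EOT as an analysis visit for the DPC and OLE periods, so that the EOT ECG is tabulated in both.
- **Injectable SRL:** flag values taken after it was restarted, and show the tables with and without them.
- **Later off-drug visits:** keep them out of these tables, in listings or a separate table.
- **6.9.3 and 6.9.4:** leave the laboratory and vital-sign tables on the last on-drug value where one exists.
- **Consistency:** reconcile SAP 6.9 with Protocol 8.4.8.

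The cost is SAP wording and table programming, because the EOT assessments are already in the visit schedule. The small downside is that some values will have been taken days after the last dose, which the window limits.
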